	Group 3: Participants will continue to receive their background lipid lowering therapy, plus inclisiran for injection (delivered in an injection-only model), plus behavioural support.	
Efficacy assessments	A capillary blood sample will be taken for immediate analysis of the participant's lipid profile for assessment of efficacy. This will be performed at screening/baseline visit, day 90 and end of study (EOS) visit.	
	 Parameters to be assessed include: Non-HDL (calculated) LDL-C calculated using Friedewald 	
Key safety assessments	Adverse events will be collected throughout the study period using ConneXon data platform.	
	The AEs to be recorded are:	
	 All SAEs whatever the causal relationship to the to the Investigational Medicinal Product (IMP) or to a procedure required by the study protocol AEs leading to treatment discontinuation 	
Other assessments	Comparisons between the Group 2 and 3 and the different delivery models will analyse whether the 'supported inclisiran' arm generates greater benefits than the injection only model in terms of outcomes other than LDL cholesterol: patient adherence, acceptability (both through PROMs) and wider cardiovascular risk. A process evaluation will build on and extend the study results, providing in-depth data on adherence and acceptability (through detailed interviews) with patients and professionals involved in the trial.	
Data analysis	The primary effectiveness objective of this study is to demonstrate superiorit each inclisiran arm compared to standard of care + behavioural support in te of the percentage change from baseline in LDL-C to Day 270 in adults elevated LDL-C. The statistical hypotheses that will be tested for each inclis arm are as follows:	
	• H0: The difference between participants treated with inclisiran (+/- behavioural support) and standard of care + behavioural support in the least squares mean percentage change from baseline to the Day 270 visit in LDL-C= 0	
	 Ha: The difference between participants treated with inclisiran (+/- behavioural support) and standard of care + behavioural support in the least squares mean percentage change from baseline to the Day 270 visit in LDL-C < 0 	

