6.4 Additional treatment guidance

6.4.1 Treatment compliance

Participants assigned to Group 1 and Group 3 (See Section 6.1.3) will receive monthly telephone based behavioural support (see Appendix 1). As part of this programme, compliance will be promoted in regard to their regular prescribed medication, including lipid lowering

therapy. Participants in Group 2 and Group 3 (See Section 6.1.3) will be reminded to attend or be available for each administration of the study drug by the investigator or designated person. Participants will be encouraged to contact their GP practice if they miss their appointment. In addition to this participants may receive SMS text reminders for their appointments from their GP practice, as is common with clinical practice.

Adherence with study medication will be based on analysis of medications dispensed (for standard of care treatment) and administered (for inclisiran treatment) during the study.

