12.5 Analysis of secondary endpoints/estimands

12.5.1 Efficacy and/or Pharmacodynamic endpoint(s)

The following are key secondary efficacy endpoints:

- Mean difference in total score using the validated CSQ-8 (Client Satisfaction Questionnaire) administered after treatment at day 90.
- Mean difference in total score using the validated Patient Activation Measure (PAM) questionnaire administered after treatment at day 90.
- Measures of adherence to cardiovascular disease self-management using the validated Patient Activation Measure (PAM) questionnaire administered after treatment at day 90 and using assessment of medication adherence during the study period.
- A process evaluation conducted using the Consolidated Framework for Implementation Research (CFIR)

The analysis methodology used for the process evaluation is described separately in Section 4.3.

The key secondary endpoints will be analysed using an ANCOVA model that includes treatment and baseline value (as appropriate). Full details, including possible sensitivity analyses, will be provided in the SAP.

Descriptive summaries by treatment group will be presented.

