#### 2.6.1.2 The PAM PROMs Questionnaire

This study will use the 13-point PAM questionnaire, which will be complimented by data on medication adherence to Inclisiran or standard of care recorded during the trial. The 13 item PAM consists of 13 statements relating to patients beliefs about health care, confidence in their management of health related tasks, and self-assessed knowledge of their condition.

For each statement patients are required to say how much they either agree or disagree on a response scale of 1–4, where 1 represents "strongly disagree" and 4 represents "strongly agree". Patients may also answer "non-applicable" which is scored as 0. A total score is created by summing the scores for the 13 statements and multiplying by 13/(13-n) where n is the number of statements answered as "non-applicable" or missing. The total is rounded to the nearest integer. The total score in the range [13,52] is then converted to a score in the range [0,100] using a calibration table. Note that if n>3, the calibrated score defaults to 51.

The continuous PAM scores are then categorized into four levels for descriptive purposes: according to the materials supplied by Insignia, scores less than 47.1 are level 1, scores between

47.1 and 53.2 are level 2, scores between 53.3 and 70.2 are level 3, and scores above 70.2 are level 4.

The following endpoints will be analyzed with PAM PROMs Questionnaire data.

- Endpoint: Mean difference in total score using the validated Patient Activation Measure (PAM) questionnaire administered after treatment at day 90. Summary measure: Difference between treatment groups in mean change in total scores from baseline to Day 90.
- Endpoint: Measures of adherence to cardiovascular disease self-management using the validated Patient Activation Measure (PAM) questionnaire administered after treatment at day 90 and using assessment of medication adherence during the study period. Summary measure: The frequency and percentages of subjects in the four levels of the PAM scores (below) will be summarized. Note that highly activated patients (level 3 and level 4) are more likely to adhere to cardiovascular self-management and thus medication adherence.

Level 1: Disengaged and overwhelmed

Level 2: Become aware but still struggling

Level 3: Taking action

Level 4: Maintaining behaviors and pushinng further

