#### 2.6.2 Statistical hypothesis, model, and method of analysis

The key secondary variables will be analyzed as follows:

- Mean difference in total score using the validated CSQ-8 (Client Satisfaction Questionnaire) administered after treatment at day 90 between the groups will be analyzed using ANOVA. The test statistics, mean difference, 95% confidence interval and the p-value obtained using the ANOVA will be presented.
- The comparison between inclisiran and inclisiran + behavioural support also will be done and presented as mentioned above. Inclisiran arm will be considered as control for this analysis.
- The descriptive statistics for the total CSQ score will be provided for each treatment group.
- Mean difference in total score using the validated Patient Activation Measure (PAM) questionnaire administered after treatment from baseline today 90 will be analyzed using ANCOVA model. ANCOVA model which assumes unequal variances for treatment group will be used. The model will include the fixed effects of treatment group with baseline total scores as a covariate. The estimate and corresponding 2-sided 95% confidence intervals of mean difference between treatment groups will be calculated. p-value for hypothesis test for mean difference will also be provided. The FAS will be used for this analysis.
- The comparison between inclisiran and inclisiran + behavioural support also will be done and presented as mentioned above. Inclisiran arm will be considered as control for this analysis.

| Novartis | Confidential | Page 22 of 37           |
|----------|--------------|-------------------------|
| SAP      |              | Study No. CKJX839A1GB01 |

• Measures of adherence to cardiovascular disease self-management using the validated Patient Activation Measure (PAM) questionnaire administered after treatment at day 90 and using assessment of medication adherence during the study period will be summarized by providing the frequency and percentages of subjects in the four levels of the PAM scores (below) by visit and treatment. Note, highly activated patients (level 3 and level 4) are more likely to adhere to cardiovascular self-management and thus medication adherence.

Level 1: Disengaged and overwhelmed

Level 2: Become aware but still struggling

Level 3: Taking action

Level 4: Maintaining behaviors and pushinng further

• Also frequency and percentage of subjects completed each item of PAM questionnaire will be summarized by visit and treatement.

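### The SAP answers the adherence endpoint with PAM levels alone: no medication-adherence measure or between-arm comparison is tied to it, notably for background lipid-lowering therapy

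*SAP*

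**What the plan says.** Protocol 12.5.1 and SAP 2.6.1 list a key secondary endpoint on adherence to cardiovascular self-management. It has two sources: PAM at Day 90, and a further part worded "using assessment of medication adherence during the study period". Protocol 6.4.1 says where that further part comes from: adherence is "based on analysis of medications dispensed (for standard of care treatment) and administered (for inclisiran treatment) during the study".

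The SAP repeats the two-part title and states that PAM is an instrument "which will be complimented by data on medication adherence to Inclisiran or standard of care recorded during the trial". The summary measure it then gives in 2.6.1.2 is: "The frequency and percentages of subjects in the four levels of the PAM scores (below) will be summarized". The method in 2.6.2 is the same: the endpoint "will be summarized by providing the frequency and percentages of subjects in the four levels of the PAM scores", by visit and treatment. Beside it stands the note that "highly activated patients (level 3 and level 4) are more likely to adhere to cardiovascular self-management and thus medication adherence". SAP 1.2 has the same content.

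The protocol is not of one mind. Under other assessments, the protocol summary describes the comparison of Groups 2 and 3 as covering "patient adherence, acceptability (both through PROMs) and wider cardiovascular risk".

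**The concern.** The endpoint asks for two things and the SAP delivers one. PAM measures beliefs, confidence and self-assessed knowledge. Its levels are cut-points of the score already analysed as the preceding key secondary endpoint, so they add no information on medicine-taking. Followed as written, the SAP puts an activation table under an adherence heading, with a sentence inviting the reader to treat one as the other.

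Adherence is part of why the trial is run. Protocol 1.1.5 gives poor real-world adherence as a motive for the dosing regimen. Protocol 6.4.1 and Appendix 1 make promotion of medication adherence part of the behavioural support given to Groups 1 and 3. Whether that support changes the use of background lipid-lowering therapy is a natural question for this endpoint, and no measure is set up to answer it.

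**Working it through.** **1. Endpoint against summary measure.**
- Required (Protocol 12.5.1, SAP 2.6.1): PAM at Day 90, plus medication adherence during the study.
- Source of the second part (Protocol 6.4.1): medicines dispensed for standard of care; doses administered for inclisiran.
- Delivered (SAP 1.2, 2.6.1.2, 2.6.2): frequencies in PAM levels 1 to 4. These sections define no adherence variable, observation period or between-arm contrast.

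**2. Can PAM levels carry the second part?** None of the 13 items in Protocol Appendix 3 asks whether medicines were taken. Table 8-1 schedules PAM at screening and Day 90 only, so it says nothing about Day 90 to Day 270, which is 180 of the 270 days.

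**3. What the treatment tables supply.** SAP 2.4.1 summarises doses given, exposure, and participants dosed by visit and arm. Its inclisiran exposure formula is min(last dose − first dose + 180, last visit − first dose). For a last visit at Day 270:
- doses on Day 1 and Day 90: min(89 + 180, 269) = 269 days;
- Day 1 dose only: min(0 + 180, 269) = 180 days.

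Inclisiran compliance is therefore partly visible. Three limits remain:
- SAP 2.4 puts these summaries on the Safety Set, which requires at least one dose of study treatment (SAP 2.2). Study treatment is inclisiran (Protocol glossary and 6.1). Read literally, all of Group 1 is omitted, as is anyone in Groups 2 or 3 who was never dosed.
- Lipid-lowering exposure runs from first to last dose, capped at the last visit. It ignores gaps and does not start at randomisation. It also needs a last-dose date, while SAP 2.4.2 says the medical-record system has no medication end date. The readable text gives no substitute.
- SAP 2.4.2 counts therapy newly added or changed after randomisation. That describes regimen changes, not continued use.

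**4. Sample size.** The plan gives no adherence figure. Its own figure, 300 per arm, rests on CSQ-8 and PAM with effect size 0.3, 90% power, one-sided 0.025 and 20% drop-out:
- n = 2(1.960 + 1.282)² / 0.3² = 234 evaluable per arm after rounding up;
- 234 / (1 − 0.2) = 293, within 3% of 300.

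The stated size reproduces and does not depend on the adherence gap. Evaluable number after drop-out: 300 × 0.8 = 240 per arm.

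**5. Attainable precision (illustration).** The documents give no adherence rate, so p is assumed equal in both arms. Half-width of the 95% CI for a difference in proportions = 1.96 × √(2p(1 − p)/n):

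| Assumed p | n = 240 per arm | n = 300 per arm |
|---|---|---|
| 0.5 | 8.9 points | 8.0 points |
| 0.8 | 7.2 points | 6.4 points |

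These apply to a binary measure, not to proportion of days covered. They show what could be learned; they do not measure an error in the plan.

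**The case against.** A reader might infer that the dispensing and dosing data are never analysed and that the adherence question goes wholly unanswered. The documents do not support that. SAP 2.4.1, whose heading includes compliance, tabulates inclisiran dosing by visit and arm. SAP 2.4.2 summarises lipid-lowering therapy at baseline and its later changes. The process evaluation collects interview data on adherence.

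Nor is PAM out of place. The first part of the endpoint names it, and Appendix 3 links the lowest level with poor adherence. Some items concern following through on treatment and keeping up lifestyle changes. The SAP sentence is a note beside a descriptive table, with no test or decision rule on adherence attached. The protocol summary itself assigns the Group 2 versus 3 adherence comparison to questionnaires, so the SAP can be said to follow one of two conflicting protocol statements.

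It is also possible that Group 1 was meant to appear in the treatment tables, since an exposure formula for lipid-lowering therapy is given. SAP 2.9, 2.10 and section 4 are partly blank in the public copy, so an adherence analysis there cannot be ruled out.

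All of this narrows the point without removing it. Descriptive dosing tables are not the endpoint's analysis and give no between-arm estimate. The sections that define the endpoint are readable and contain no medication measure.

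**Conclusion.** The concern holds in limited form. The medication-adherence component of one of the three quantitative key secondary endpoints in SAP 2.6.1 has no summary measure, and PAM levels stand in for it. For inclisiran the gap is modest, because doses are tabulated, though without a contrast or confidence interval. For background lipid-lowering therapy it is substantive: no workable comparison across the three arms exists. Protocol 6.4.1 and the protocol summary also disagree on how adherence is assessed.

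This rests on a literal reading of the Safety Set and on the blank SAP text holding no adherence analysis. The primary LDL-C analysis and the sample size are unaffected. The precision figures in the working depend on assumed rates of 50% to 80%; a smaller denominator for background therapy would widen them.

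**What to change.** In SAP 1.2, 2.6.1.2 and 2.6.2, keep PAM levels as an activation summary and delete the inference to medication adherence. Add two measures:

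- **Background therapy.** Among FAS participants on lipid-lowering therapy at baseline, in all three arms: the proportion with a lipid-lowering issue or dispensing record in each 90-day interval from randomisation to Day 270 (three intervals). Restricting to those on therapy at baseline matters because Protocol 6.1.2 admits participants who cannot tolerate it. Use proportion of days covered only if quantity is confirmed to be in the medical-record extract. Report between-arm differences with 95% CIs; 3 versus 2 is the comparison the protocol names.
- **Inclisiran.** Among FAS participants in Groups 2 and 3: the proportion who received both scheduled doses, 3 versus 2 with a 95% CI.

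Reconcile the protocol summary with Protocol 6.4.1. If the sponsor prefers to drop the medication component, say so openly in SAP section 4.

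The cost is SAP wording and modest programming on medication and dosing records the trial already collects. The downside is that issue records only approximate medicine-taking.

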#### 2.6.2 Statistical hypothesis, model, and method of analysis

The key secondary variables will be analyzed as follows:

- Mean difference in total score using the validated CSQ-8 (Client Satisfaction Questionnaire) administered after treatment at day 90 between the groups will be analyzed using ANOVA. The test statistics, mean difference, 95% confidence interval and the p-value obtained using the ANOVA will be presented.
- The comparison between inclisiran and inclisiran + behavioural support also will be done and presented as mentioned above. Inclisiran arm will be considered as control for this analysis.
- The descriptive statistics for the total CSQ score will be provided for each treatment group.
- Mean difference in total score using the validated Patient Activation Measure (PAM) questionnaire administered after treatment from baseline today 90 will be analyzed using ANCOVA model. ANCOVA model which assumes unequal variances for treatment group will be used. The model will include the fixed effects of treatment group with baseline total scores as a covariate. The estimate and corresponding 2-sided 95% confidence intervals of mean difference between treatment groups will be calculated. p-value for hypothesis test for mean difference will also be provided. The FAS will be used for this analysis.
- The comparison between inclisiran and inclisiran + behavioural support also will be done and presented as mentioned above. Inclisiran arm will be considered as control for this analysis.

| Novartis | Confidential | Page 22 of 37           |
|----------|--------------|-------------------------|
| SAP      |              | Study No. CKJX839A1GB01 |

• Measures of adherence to cardiovascular disease self-management using the validated Patient Activation Measure (PAM) questionnaire administered after treatment at day 90 and using assessment of medication adherence during the study period will be summarized by providing the frequency and percentages of subjects in the four levels of the PAM scores (below) by visit and treatment. Note, highly activated patients (level 3 and level 4) are more likely to adhere to cardiovascular self-management and thus medication adherence.

Level 1: Disengaged and overwhelmed

Level 2: Become aware but still struggling

Level 3: Taking action

Level 4: Maintaining behaviors and pushinng further

• Also frequency and percentage of subjects completed each item of PAM questionnaire will be summarized by visit and treatement.

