4.3.3.4 Data analysis

Initial analysis will follow a similar approach to the provider interviews above from which a blueprint of how to implement inclisiran more widely will be generated. This blueprint will combine data from all three levels of inquiry with implementation costs and outcomes to identify the 'core enabling ingredients' and preferred model of service delivery deemed necessary to support the uptake of inclisiran across the NHS.

Implementation costs will be largely made up of the time and resources required to deliver each inclisiran model. The costs of health professional input will be based on national average rates **PSSRU** (Personal Social Services Research using Unit) estimates (https://www.pssru.ac.uk/project-pages/unit-costs/). The length of each clinical encounter will be collected and coded to each practice, and costed on the basis of the full economic costs of the staff involved. Estimates of the additional time required from the general practice staff will be obtained. These unit costs will then be multiplied by the time spent recorded in the call log or timesheet during the trial period to estimate the costs of delivering each model. The data will be used to construct models of the potential implementation costs from a Clinical Commissioning Group perspective and how these costs may vary with different levels of implementation.

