Participants randomised to Group 2 and Group 3 will be administered a single SC 300mg inclisiran injection at predefined time points described in the visit schedule and assessments (Section 8). The HCP who administers each dose of inclisiran for participants randomised to Group 2 and Group 3 will be decided by the GP PI at each site, in common with clinical practice within that primary care setting. Therefore, inclisiran may be administered by a GP, practice nurse, practice pharmacist or delivered and administered by a homecare team (Figure 4-2). Participants receiving inclisiran administered by a GP, practice nurse or practice pharmacist will be required to attend their GP practice or local Hub for administration of the study drug. The homecare team will administer inclisiran to participants in their own home setting. These visits will be performed by experienced HCPs with anaphylaxis training and following local guidelines and SOPs. This approach to recruitment is to enable participants who ordinarily may be unable to attend the GP practice due to a debilitating condition or travel burden to be involved

in the study. If a participant receives the study medication at home the lipid profile test at Day 90 will also be performed at home.

In the event of a global health disruption event, such as a pandemic/epidemic (e.g. COVID-19), that limits or prevents access to the GP practice, an alternative qualified research site already participating in the study may be used to conduct study activities per protocol.

All participants will receive a point of care blood test (see visit schedule in Section 8) to assess changes in lipid profile during the study.

All participants will be required to complete patient reported outcomes (PROMs) as part of the study. The CSQ-8 and PAM validated PROMs questionnaires and/or the

(Appendix 2) will be provided to the study participant following their clinic visit. The participant is to complete the questionnaire away from the clinical setting, thus providing the participant with sufficient space and time. Participant's refusal to complete all or any part of a PROM should be documented in the study data capture system and should not be captured as a protocol deviation.

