16.1 Appendix 1: Behavioural Support Programme

To determine whether additional supported care can improve health behaviour, self-efficacy and health status, consented participants randomised to Group 1 and Group 3 will receive monthly telephone-based support call.

Behavioural Support will consist of a telephone-based lifestyle intervention to motivate and support participants to make effective choices for improving self-management including behaviour change, goal setting and empowerment.

This model of behavioral support is based on a well-established service involving non-clinical health advisors trained in motivational interviewing techniques. This was first developed from the Pro-active Call Centre Treatment Support randomised controlled trial (Young et al 2005) which demonstrated that pro-active healthcare adviser support improves glucose control in people with type 2 diabetes.

The telephone-based, lifestyle intervention will provide monthly support to enable participants to make positive behaviour changes. An initial call will be delivered by a health advisor and is focused on action planning to ensure each participant understands their diagnosis, the importance of reducing CV risk and taking medications correctly and how they can reduce their own risk. A lifestyle goal is then set together to help begin to achieve this, and participants will receive a pack of information, on CV disease and advice on healthy eating to help participants with goal setting and facilitate their understanding of risk.

The remainder of the programme is delivered by dedicated health advisors and consists of monthly telephone calls sequentially covering diet, exercise, medication and where necessary additional advice about glucose management and smoking cessation.

The behavioural support programme will be provided by a qualified medical support team.

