## 3 Sample size calculation

The primary effectiveness endpoint of the study is percent change of LDL-C from baseline. However, the sample size is driven by patient experience (CSQ-8) and patient activation (PAM); two key secondary outcomes in this trial.

The trial has been powered to detect differences equivalent to a Cohen's effect size of 0.3, approximating a 'small-to-medium' effect in conventional terms

A sample size of 300 patients per arm would be able to detect this effect size with 90% power using a one-sided significance level of 0.025 (this includes a 20% allowance for drop-out in this primary care setting).

This sample size could also detect a reduction of at least 10% change of LDL-C from baseline in the inclisiran group compared to the control group (assuming a standard deviation of 30% in the control group and 20% in the inclisiran group based on observed results from previous inclisiran studies).

The total sample size for the study will be 900 participants.

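### The CSQ-8 and PAM models ignore health advisors, who coach Groups 1 and 3 but not Group 2, so the intervals for Group 3 v 2 and Group 2 v 1 are too narrow if scores cluster by advisor

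*SAP*

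**What the plan says.** **Models.** SAP 2.6.2 states that the mean difference in CSQ-8 total score "administered after treatment at day 90 between the groups will be analyzed using ANOVA". It names no factor other than treatment group. PAM gets an ANCOVA with treatment and baseline PAM, allowing a different variance in each arm. Besides the comparisons with control, Group 3 is compared with Group 2 on both scales, with an interval and a p-value. Protocol 12.5.1 likewise names only treatment and baseline. For these endpoints neither document mentions a practice or advisor effect, a cluster-robust SE, an ICC or a sensitivity analysis for clustering.

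**Delivery.** Protocol Appendix 1 gives the telephone programme to Groups 1 and 3 only. After an action-planning call, "The remainder of the programme is delivered by dedicated health advisors and consists of monthly telephone calls". The number of advisors, their caseload and whether a participant keeps the same advisor are not stated. For Groups 2 and 3, the person who injects "will be decided by the GP PI at each site, in common with clinical practice within that primary care setting" (Protocol 4.5).

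**Records.** For costing, Protocol 4.3.3.4 has unit costs "multiplied by the time spent recorded in the call log or timesheet during the trial period". It does not say that the log identifies the advisor.

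**Role of the endpoints.** Protocol 12.8 and SAP 3 base the sample size on CSQ-8 and PAM, not on LDL-C.

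**The concern.** Participants coached by the same advisor share whatever that advisor does well or badly. CSQ-8 asks about satisfaction with a service from a particular provider or setting, so it is directly exposed. PAM is not a service rating: it records the participant's own beliefs, confidence and knowledge. It can still cluster by advisor, because the calls aim to change what its items ask about, such as knowing one's medications and keeping up lifestyle changes.

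Where only one of two compared arms has advisors, advisor variance enters one mean and has nothing to cancel against. That is so for Group 3 v 2 and Group 2 v 1. Group 3 v 2 isolates what behavioural support adds to the injection, which the protocol summary names as a comparison of interest. An ANOVA or ANCOVA on independent scores leaves this variance out of the SE. The arm-specific variances planned for PAM do not help: they allow different spread, not correlation within a caseload.

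**Working it through.** **1. Reproduce the plan's figure.** Inputs from SAP 3: "A sample size of 300 patients per arm"; a standardised difference of 0.3 ("effect size of 0.3, approximating" a small-to-medium effect); "with 90% power using a one-sided significance level of 0.025"; and "this includes a 20% allowance for drop-out in this primary care setting".

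- n = 2(1.960 + 1.282)²/0.3² = 2 × 10.51/0.09 = 233.5, so 234 evaluable per arm.
- 234/0.8 = 292.5, so 293 per arm, against the stated 300.
- Evaluable: 300 × 0.8 = 240. Power = Φ(0.3/√(2/240) − 1.96) = Φ(3.286 − 1.960) = 90.8%.

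The stated size therefore reproduces with a design effect of 1: neither the design nor the analysis allows for clustering.

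**2. One arm with advisors, one without.** Set the SD to 1, with k advisors in the coached arm, m = 240/k participants each, and advisor ICC ρ. Both k and ρ are assumptions.

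- Design effect in the coached arm: DE = 1 + (m − 1)ρ. In Group 2 it is 1.
- Reported SE = √(2/240). True SE = √((1 + DE)/240). Ratio = √((1 + DE)/2).
- Actual two-sided error of a nominal 5% test = 2[1 − Φ(1.96/ratio)].
- Power with the true SE = Φ(0.3/true SE − 1.96).

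For k = 6 and ρ = 0.02: m = 40; DE = 1 + 39 × 0.02 = 1.78; ratio = √1.39 = 1.18; error = 9.6%; true SE = √(2.78/240) = 0.108; power = 80%.

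| Advisors | ICC | m | DE | SE ratio | Error | Power |
|---|---|---|---|---|---|---|
| 20 | 0.01 | 12 | 1.11 | 1.03 | 5.6% | 89% |
| 20 | 0.02 | 12 | 1.22 | 1.05 | 6.3% | 88% |
| 20 | 0.05 | 12 | 1.55 | 1.13 | 8.3% | 83% |
| 10 | 0.02 | 24 | 1.46 | 1.11 | 7.7% | 84% |
| 6 | 0.02 | 40 | 1.78 | 1.18 | 9.6% | 80% |
| 6 | 0.05 | 40 | 2.95 | 1.41 | 16.3% | 65% |
| 4 | 0.05 | 60 | 3.95 | 1.57 | 21.3% | 55% |

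The power column uses the normal critical value. With few advisors the proper t reference would lower it further.

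**3. Check by simulation** (unadjusted comparison, 240 per arm, 30 practices, practice ICC 0.05, advisor ICC 0.02). With advisors in one arm only, the nominal 5% test rejected in 9.7% of runs for 6 advisors and 6.5% for 20, close to the formula's 9.6% and 6.3%. With the same 6 advisors serving both arms it rejected in 5.0%, which is the Group 3 v 1 case if advisors are shared.

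**4. Practice.** Protocol 6.2.2 randomises individuals, so each practice is expected to hold all arms and a shared practice effect largely cancels. If arms are balanced within practice, the correct SE is √(1 − ICC) times the reported one: 0.995, 0.975 and 0.949 at ICC 0.01, 0.05 and 0.10. In simulation the unadjusted test rejected in 4.8-5.3% of runs (simple randomisation) and 4.5-4.7% (balanced) at ICC 0.05, and in 5.0% and 4.0% at ICC 0.10. The planned test is about right or slightly conservative. A practice-by-arm variance of 0.02 gave 5.8%, a mild excess.

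**The case against.** **The size rests on assumptions.** This stands. The range runs from trivial to serious, and nothing in the documents favours 6 to 10 advisors or an ICC of 0.02. About three monthly calls would have taken place by Day 90, so the ICC could be small. What does not depend on the assumed values is the direction: any positive ICC with several participants per advisor makes the reported SE too small.

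**Participants may not be nested in advisors.** Appendix 1 speaks of advisors in the plural and promises no continuity. If calls were shared, a single advisor effect per participant is undefined and the table does not apply as it stands. This changes the form of the model; it does not make the scores independent.

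**The inference could be limited to the advisors actually used.** Advisor variance would then be irrelevant. But the study is meant to inform delivery across the NHS, where other people would make the calls.

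**The consequences are limited.** The primary LDL-C analysis is outside this point, and the Holm procedure covers only that endpoint. No multiplicity-controlled claim rests on these p-values. Even so, these two outcomes set the sample size.

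**A mixed model is no complete cure with few advisors.** In a simulation with an advisor term but no small-sample correction, 6 advisors at ICC 0.02 gave 5.9% error, with a zero variance estimate in 26% of runs; 4 advisors at ICC 0.05 gave 9.1%. This is a reason to require corrected degrees of freedom, not to keep a model that gives 9.6% and 21.3% in the same cases.

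**Conclusion.** The point holds for two of the three contrasts. For Group 3 v 2 and Group 2 v 1, on both CSQ-8 and PAM, the planned intervals are too narrow and the error is above 5% if the advisor ICC is positive and advisors are seen as a sample of those who could deliver the programme. Under the assumed values the true SE is 3% to 57% larger than the reported one, and 11-18% larger with 10 to 6 advisors at ICC 0.02. The size cannot be settled from the documents. Group 3 v 1 is about unaffected if the same advisors serve both arms, which the documents do not state.

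A reader might infer three stronger things, and none is supported:

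- **That leaving out practice makes the error bars wrong everywhere.** Randomisation is individual, so a practice intercept offers at most a small gain in precision. That the injector is chosen site by site does not show that satisfaction differs between practices.
- **That PAM clusters because it rates a service.** It does not rate one; the argument for PAM is that coaching targets it.
- **That the call log already supplies an advisor identifier.** The protocol mentions the log only for time spent.

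**What to change.** Before database lock, ask the programme provider whether advisor identity was recorded for each call, and whether each participant had one main advisor.

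Then pre-specify in SAP 2.6.2, at least as a sensitivity analysis for Group 3 v 2 and Group 2 v 1, a partially nested mixed model for CSQ-8 and PAM with:

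- treatment, plus baseline PAM in the PAM model (further covariates such as age or sex are not needed for this purpose);
- a random advisor effect in Groups 1 and 3 only, using the main advisor, or multiple membership if calls were shared;
- arm-specific residual variances, as already planned for PAM;
- optionally, a random practice intercept (the centre number is part of the participant number, Protocol 6.2.1);
- Satterthwaite or Kenward-Roger degrees of freedom.

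Report the number of advisors, their caseloads and the advisor ICC.

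**Cost.** A short SAP addition, some code and a link from advisor ID to the analysis file. Intervals for the Group 2 contrasts will be wider, and the advisor variance will be imprecise if advisors are few. Protocol Amendment 2 reports 900 participants randomised by 15 July 2022, so an identifier not captured at the time may be unrecoverable. In that case the model cannot be fitted. The report should then say so and can show the Group 2 contrasts under a range of assumed ICCs, given the number of advisors.
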